7 STUDY PLAN

The study will be a prospective, multi-center, non-blinded, randomized, non-inferiority study comparing the HeartMate III LVAS to the HeartMate II LVAS. Short term use of the device will be evaluated when Subjects have been supported for 6 months, transplanted or explanted for recovery, whichever occurs first. Long term use of the device will be evaluated when Subjects have been followed for 24 months, transplanted or explanted for recovery, whichever occurs first.

- a. **Missing Values and Data Conventions:** Every effort will be made to collect all required data. Missing primary endpoints will be imputed using multiple imputation techniques. Missing secondary endpoints will not be imputed, except as described below.
- b. **Multiplicity Adjustments:** No adjustments for multiplicity will be made in the analysis of secondary endpoints. No statistical claims will be made concerning secondary endpoints.

8 STATISTICAL PROCEDURES:

The HM III study is a prospective, multicenter, non-blinded, randomized study to test the success of the HM III LVAS for short term hemodynamic support, such as a bridge to cardiac transplant (BTT) or myocardial recovery, or as long term support, such as destination therapy (DT).

Since the device must be surgically implanted, the investigator cannot be blinded to the treatment. Similarly, since the Subject must be trained on driveline care and responses to warning alarms, the Subject cannot be blinded to treatment. The study design will allow for a scientifically rigorous examination of the performance and safety of the device.

In general, continuous data will be presented as the number of Subjects, mean with standard deviation, and median with minimum and maximum values. Categorical data will be reported as frequencies and percentages. Adverse events will also be reported as rates per patient year. Only adverse events that occur after the start of the implant procedure will be analyzed. Survival data will be presented using the Kaplan-Meier product limit method, as well as the percentage of Subjects who successfully reach the pre-defined study primary endpoint.

Data will be analyzed using the intent-to-treat method (ITT) defined as all randomized Subjects. Every effort will be made to avoid cross-over but in the event they occur, data will also be analyzed “as randomized” and Per Protocol for efficacy analysis and “as treated” for safety analysis and all other secondary endpoints.

Statistical analysis will be performed using SAS version 9.1 or higher.

8.1 Analysis Population

8.1.1 Intent-to-treat: All Randomized Subjects

This is the primary analysis population for the primary endpoint. Subjects are analyzed under the treatment to which they were randomized.

8.1.2 As Treated: All Treated Subjects

This is the primary analysis population for the secondary endpoints. Subjects are analyzed under the treatment they actually receive.

8.1.3 As Randomized: All Treated Subjects

This population includes only the Subjects who receive the treatment they were randomized to.

8.1.4 Per Protocol:

As Randomized patients who meet all protocol inclusion and exclusion criteria and are free of major protocol violations. Major protocol violations include:

1. Patients who sign consent after randomization or patients who sign an unapproved consent form
2. Implantation of the VAD using a technique other than sternotomy
3. Missing > 2 pre-specified visits after initial discharge
4. Missing data that may affect the primary outcome:
 - i. Stroke reported but MRS never provided
 - ii. Transplant or explant prior to a study endpoint but the reason for the procedure is not reported

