5 STUDY DESIGN

The study will be prospective, multi-center, unblinded, randomized, controlled, non-inferiority study, comparing the HM3 LVAS to the HM II LVAS. Short term use of the device will be evaluated when Subjects have been supported for 6 months. Long term use of the device will be evaluated when Subjects have been followed for 24 months.

Subjects who receive a device exchange to any device other than HM II or HM3, at any time during the study, will be withdrawn from the study and will not be followed.

[figure not shown]
This study will be conducted as a staged pivotal study that includes a pre-specified early assessment for safety that is consistent with FDA's new Guidance for staged approval process, and in accordance with applicable local and federal regulations as specified in 21 CFR part 812.

During the early safety phase of the pivotal study, up to 5 centers in the United States (U.S.) will be initiated to enroll up to 10 randomized HM3 Subjects. A pre-specified analysis for safety will be performed after the first 10 randomized HM3 Subjects have completed 30 day follow-up. The results of this early safety analysis will be reviewed by the Data Safety Monitoring Board (DSMB), after which the DSMB report, along with supporting safety data from the HM3 CE Mark study will be sent to FDA as an IDE supplement, with a request to gain full IDE approval to expand the study to up to a total of 60 centers in the U.S. The first 5 U.S. centers will continue to enroll up to a total of 30 subjects (including those in the early safety analysis) during FDA's review of this IDE Supplement.

The study will include an adaptive design which will be used, if required to adjust the sample size at a pre-specified time during the study.

In addition to the primary study endpoint, the study will include a powered secondary endpoint to provide supplemental data for HM3 labeling.

Figure 2 – MOMENTUM 3 IDE Study Flow

Total sample size = 1028 (randomized 1:1).

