² Vital Signs include: height (only at baseline), weight, temperature, respiratory rate, heart rate, blood pressure and mean arterial pressure.

³ Hemodynamic Measurements include: Pulmonary Capillary Wedge Pressure, Pulmonary Arterial Systolic Pressure, Pulmonary Arterial Diastolic Pressure, Pulmonary Arterial Mean Pressure, Central Venous Pressure, Cardiac Index, Cardiac Output, Pulmonary Vascular Resistance, Right Atrial pressure, and Left Atrial pressure (LAP only if available).

⁴ Post Implant or during implant procedure.

⁵ Must be performed by an independent assessor.

⁶ Required only if a stroke has occurred and 60 days post-stroke.

Thoratec® Corporation
MOMENTUM 3
IDE Clinical Study Protocol

⁷ HM II and HM3 Pump Parameters include: Pump Flow, Pump Speed, Pulsatility Index and Pump Power.

⁸ Pump Log Files include: Pump Period Log, Pump Event Log, Controller Period Log, and Controller Event Log.

⁹ If Subject is on inotropes at the time of screening/baseline, list how long the Subject has been on inotropes.

¹⁰ If Subject is able. If Subject is unable to perform, must provide reason this was not done.

¹¹ At the time of implant and as defined by INTERMACS; refer to Appendix 6.

¹² To be collected any time subject is rehospitalized.

¹³ Images to be submitted to Thoratec.

¹⁴ In addition to defined scheduled collection of pump parameters and pump logs, they must also be submitted when any pump-related or possibly related AE or malfunction occurs.

¹⁵ Post-operative TEE is also acceptable; can be performed POD 0 (post-implant) + 2 days

¹⁶ AP view for HM3 subjects; feeding tube view for HM II subjects

¹⁷ Randomization should occur as close as possible to the implant date; if possible, within 72 hours.

¹⁸ INTERMACS profile to be assessed immediately prior to implantation

¹⁹ Must be performed by an independent assessor; defined as an independent, trained, and certified clinician

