8.2 Study Hypothesis

8.2.1 Short Term Support:

The short term study endpoint is a composite of survival to transplant, myocardial recovery or 6 months of support (whichever occurs first) free of a debilitating

stroke (modified Rankin Score > 3) or reoperation to replace the original pump. A Subject will be considered a success if they are:

- Electively transplanted or explanted for myocardial recovery prior to 6 months or
- Alive at 6 months, and
 - Have not experienced a stroke with a modified Rankin Score > 3, and
 - Have not received a device replacement or exchange, and
 - Have not received an urgent transplant due to a LVAS malfunction.

A Subject will be considered a failure if they:

- Expire prior to 6 months, or
- Experience a stroke with a modified Rankin Score > 3 prior to 6 months, or
- Have a device replaced or exchanged or deactivated for reasons other than myocardial recovery prior to 6 months, or
- Have received an urgent transplant due to a LVAS malfunction prior to 6 months, or
- Have withdrawn from the study for any reason prior to 6 months

HM III short term success rate will be compared to that of the HM II control in a non-inferiority manner. The null and alternative hypotheses are:

$$H_0: \pi_{HM III} \leq \pi_{HM II} - \Delta$$

$$H_A: \pi_{HM III} > \pi_{HM II} - \Delta$$

where $\pi_{HM III}$ and $\pi_{HM II}$ are the short term success rates of HM III and HM II, respectively, and where Δ is the non-inferiority margin.

8.2.2 Long Term Support:

The long term study endpoint is a composite of survival to transplant, myocardial recovery or 24 months of support (whichever occurs first) free of a debilitating stroke (modified Rankin Score > 3) or reoperation to replace the original pump.

A Subject will be considered a success if they are:

- Electively transplanted or explanted for myocardial recovery prior to 24 months or
- Alive at 24 months, and
 - Have not experienced a stroke with a modified Rankin Score > 3, and
 - Have not received a device replacement or exchange, and
 - Have not received an urgent transplant due to a device malfunction.

A Subject will be considered a failure if they:

- Expire prior to 24 months, or
- Experience a stroke with a modified Rankin Score > 3 prior to 24 months, or
- Have a device replaced or exchanged or deactivated for any reason other than myocardial recovery prior to 24 months, or
- Have received an urgent transplant due to a LVAS malfunction prior to 24 months, or

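### The SAP's Per Protocol rules can remove subjects who are already definite primary-endpoint failures, because missed visits are counted after the outcome is settled

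*SAP*

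**What the plan says.** SAP 8.1.4 defines Per Protocol as "As Randomized patients who meet all protocol inclusion and exclusion criteria and are free of major protocol violations". Two of the listed violations matter here. Item 3 is "Missing > 2 pre-specified visits after initial discharge". Item 4 is headed "Missing data that may affect the primary outcome", and its first sub-item is "Stroke reported but MRS never provided". Neither says what happens when the subject has already met a failure criterion.

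SAP 8.2.1 lists as a failure: "Have a device replaced or exchanged or deactivated for reasons other than myocardial recovery prior to 6 months". SAP 8.2.2 has the 24-month equivalent. Death, stroke with a Rankin score above 3, urgent transplant for malfunction, and withdrawal are also failures. None of these depends on attendance after the event.

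Protocol sections 5 and 22 withdraw a subject after a pump exchange only when the new device is neither an HM II nor an HM3. Such a subject "will be withdrawn from the study and will not be followed". A subject exchanged to another HM II or HM3 is not withdrawn on that ground.

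On roles, SAP 8.1.1 makes ITT the primary population for the primary endpoint. The opening text of SAP 8 adds "Per Protocol for efficacy analysis" in the sentence on cross-overs. The non-inferiority rule in SAP 8.6 does not mention Per Protocol.

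**The concern.** A Per Protocol exclusion should remove subjects whose conduct in the trial makes their outcome unreliable. Item 3 goes further. It can remove a subject whose outcome is fixed and documented, because of attendance after that outcome. Membership of the population then depends partly on what follows a primary event, in a trial where site staff and subjects know the device.

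In a non-inferiority trial, readers usually look for the Per Protocol result to agree with ITT. If established failures can drop out of it, agreement or disagreement between the two analyses is harder to interpret.

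**Working it through.** **1. Can a definite failure be removed?** The protocol synopsis schedules visits after discharge at months 1, 3, 6, 12, 18 and 24, six in all.

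- A subject attends month 1 and has the pump exchanged at month 2 for another HM II or HM3. The subject is a failure at both 6 and 24 months (SAP 8.2) and remains in follow-up (Protocol 5 and 22).
- The subject attends months 3 and 6 and misses months 12, 18 and 24. That is 3 missed visits, and 3 > 2, so item 3 removes the subject.
- Nothing about the primary outcome was missing. This case needs no disputed reading.

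**2. Where does item 3 act?** By 6 months only three visits after discharge are due (months 1, 3, 6), so more than two means all three. By 24 months it takes three of six. The rule therefore acts mainly on the 24-month analysis.

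**3. Item 4.i.** Protocol Table 2, footnote 6, says of the Rankin score: "Required only if a stroke has occurred and 60 days post-stroke". A subject with an unscored stroke and a separate pump exchange is a failure through the exchange, whatever the score would have been. The words of 4.i still remove that subject. A subject with an unscored stroke and no other event is undetermined, and 4.i fits that case.

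**4. Planning figures.** Farrington-Manning, one-sided alpha 0.025, 80% power, margin 0.10:

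n per arm = [(1.96·s0 + 0.84·s1) / (pT − pC + 0.10)]², with s0 from the restricted estimates under the null and s1 from the assumed rates.

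- 6 months (87% v 85%): restricted estimates 0.794 and 0.894; n = 137.86, so 138. The SAP states 138.
- 24 months (55% v 50%): n = 172.65, so 173. The SAP states 174, and the unpooled formula gives 174.

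The inputs are therefore read correctly. The planned sizes after the allowance for early outcomes are 147 and 183 per arm.

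**5. Effect near the margin.** The documents give no rate of such exclusions, so the number removed is assumed. Lower limit = pT − pC − 1.96·√[pT(1−pT)/nT + pC(1−pC)/nC]. This normal-approximation interval is also an assumption, because SAP 8.6 does not name the interval method. The last column is the Farrington-Manning statistic, to be compared with 1.96.

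| HM3 v HM II | Difference | SE | Lower limit | F-M z |
|---|---|---|---|---|
| 6 months, 122/147 v 125/147 | -0.0204 | 0.0427 | -10.4% | 1.84 |
| one HM3 failure removed: 122/146 v 125/147 | -0.0147 | 0.0425 | -9.8% | 1.97 |
| 24 months, 92/183 v 92/183 | 0.0000 | 0.0523 | -10.2% | 1.92 |
| one HM3 failure removed: 92/182 v 92/183 | 0.0028 | 0.0523 | -9.98% | 1.97 |
| 6 months, 123/147 v 125/147 | -0.0136 | 0.0424 | -9.7% | 2.00 |
| one HM II failure removed: 123/147 v 125/146 | -0.0194 | 0.0421 | -10.2% | 1.88 |

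One removed HM3 failure can turn a miss into a pass. One removed HM II failure can turn a pass into a miss.

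**6. Equal removal in both arms.** If a share f of failures is removed, a success rate p becomes p / [p + (1−p)(1−f)]. Put the true difference at the margin and take f = 10%.

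- 6 months, 75% v 85%: 0.75/0.975 = 76.9% and 0.85/0.985 = 86.3%. The difference is -9.4 points, and the chance of a false non-inferiority finding rises from 2.5% to 3.4%.
- 24 months, 40% v 50%: 0.40/0.94 = 42.6% and 0.50/0.95 = 52.6%. The difference is -10.1 points, and the chance is 2.4%.

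At 24 months, where item 3 mainly acts, equal removal is close to neutral. Removing three failures from HM3 alone gives 5.3% at 6 months and 3.4% at 24 months.

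**The case against.** **Per Protocol decides nothing.** This stands. ITT is primary, the non-inferiority rule does not refer to Per Protocol, and ITT keeps every failure described here. The documents also do not say that Per Protocol must confirm ITT.

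**The rules remove only failures and so favor HM3.** A reader might infer this, but the text does not support it. Item 3 also removes a subject who is alive at 24 months on the original pump, free of disabling stroke, and skipped three visits. That subject is a success. The plan also expects more replacements on HM II than on HM3, 7% against 3% at 24 months (SAP 8.16). On 183 per arm that is about 12.8 against 5.5. If exclusions follow replacements, more failures leave the control arm, which makes non-inferiority harder to show.

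**Exchange to a third device before month 3 automatically triggers item 3.** This too is tempting. It requires counting as missed those visits that the protocol no longer schedules. On that reading every death or elective transplant before the month 12 visit would also be excluded, since at least three visits would remain. Elective transplants are successes, so the reading is implausible and not one-sided. What stands is that the SAP does not state the cut-off.

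**The item 4 heading already limits 4.i.** This is largely right. Where another component settles failure, a missing score cannot affect the outcome. A stroke followed by death is a weak example in any case, because Protocol Appendix 5 defines a score of 6 as dead. The stroke-plus-exchange case remains on literal wording, and the limit should be stated.

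**Conclusion.** The point holds as a defect in the definition of a supportive population. Item 3 can remove a definite 24-month failure for later non-attendance, and item 4.i can do so if read literally. The primary ITT test and the sample size are untouched.

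The documents establish neither a fixed direction nor a size. The direction depends on the arm and on the mix of failures and successes removed. The borderline cases show sensitivity only: they assume results close to the -10% limit and one subject removed from one arm, and they do not predict the trial's result. The amendment is still worth making, because the case in step 1 of the working follows directly from the text and the correction costs almost nothing.

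**What to change.** Amend SAP 8.1.4 in two places, before any further unblinded comparison:

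- **Item 3:** count only visits due before the first primary-endpoint event, outcome (transplant, explant or death) or withdrawal. Apply the same cut-off to successes and failures and to both arms.
- **Item 4.i:** apply it only where the missing Rankin score is the sole determinant of success or failure.

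A blanket rule that no failure may ever be excluded should be avoided. It would keep failures with poor attendance before the event while excluding successes with the same attendance, which is itself selection on outcome.

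The cost is two sentences, with no new data, subjects or change in sample size. The Per Protocol success rate will differ slightly and may be lower. Subjects with an early event will have fewer visits to miss than those followed to 24 months, so the report should list Per Protocol exclusions by arm, reason and ITT outcome.

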8.2 Study Hypothesis

8.2.1 Short Term Support:

The short term study endpoint is a composite of survival to transplant, myocardial recovery or 6 months of support (whichever occurs first) free of a debilitating

stroke (modified Rankin Score > 3) or reoperation to replace the original pump. A Subject will be considered a success if they are:

- Electively transplanted or explanted for myocardial recovery prior to 6 months or
- Alive at 6 months, and
 - Have not experienced a stroke with a modified Rankin Score > 3, and
 - Have not received a device replacement or exchange, and
 - Have not received an urgent transplant due to a LVAS malfunction.

A Subject will be considered a failure if they:

- Expire prior to 6 months, or
- Experience a stroke with a modified Rankin Score > 3 prior to 6 months, or
- Have a device replaced or exchanged or deactivated for reasons other than myocardial recovery prior to 6 months, or
- Have received an urgent transplant due to a LVAS malfunction prior to 6 months, or
- Have withdrawn from the study for any reason prior to 6 months

HM III short term success rate will be compared to that of the HM II control in a non-inferiority manner. The null and alternative hypotheses are:

$$H_0: \pi_{HM III} \leq \pi_{HM II} - \Delta$$

$$H_A: \pi_{HM III} > \pi_{HM II} - \Delta$$

where $\pi_{HM III}$ and $\pi_{HM II}$ are the short term success rates of HM III and HM II, respectively, and where Δ is the non-inferiority margin.

8.2.2 Long Term Support:

The long term study endpoint is a composite of survival to transplant, myocardial recovery or 24 months of support (whichever occurs first) free of a debilitating stroke (modified Rankin Score > 3) or reoperation to replace the original pump.

A Subject will be considered a success if they are:

- Electively transplanted or explanted for myocardial recovery prior to 24 months or
- Alive at 24 months, and
 - Have not experienced a stroke with a modified Rankin Score > 3, and
 - Have not received a device replacement or exchange, and
 - Have not received an urgent transplant due to a device malfunction.

A Subject will be considered a failure if they:

- Expire prior to 24 months, or
- Experience a stroke with a modified Rankin Score > 3 prior to 24 months, or
- Have a device replaced or exchanged or deactivated for any reason other than myocardial recovery prior to 24 months, or
- Have received an urgent transplant due to a LVAS malfunction prior to 24 months, or
- Have withdrawn from the study for any reason prior to 24 months

The 24 month success rate of the HM III Subjects will be compared to the HM II control. The null and alternative hypotheses are:

$$H_0: \pi_{HM III} \leq \pi_{HM II} - \Delta$$
$$H_A: \pi_{HM III} > \pi_{HM II} - \Delta$$

where $\pi_{HM III}$ and $\pi_{HM II}$ are the long term success rates of HM III and HM II, respectively, and where Δ is the non-inferiority margin.

8.3 Randomization

Subjects will be randomized in a 1:1 fashion (1 HM III: 1 HM II). The randomization will be stratified by study center and blocked to maintain the 1:1 ratio over time. Randomization will be implemented through the Electronic Data Capture (EDC) system. Study centers will be allowed a maximum of 50 randomized Subjects. Subjects will be considered enrolled in the study upon randomization and will be included in the intent-to-treat analysis.

8.4 Sample Size

8.4.1 Assumptions

- Larger gap between the rotor and pump housing in the HM III may result in less thrombus than HM II
- Larger gap between the rotor and pump housing in the HM III may result in less pump replacement due to ingested thrombus than HM II
- HM III modular driveline may reduce pump replacements due to driveline damage or fatigue.

8.4.2 Short Term Indication

Based on a review of recent INTERMACS and Thoratec data, it is assumed that the HM II will achieve a composite success rate of 85% at 6 months. It is also assumed that the HM III will have a composite success rate of 87% due to less pump replacements at 6 months caused by thrombus or driveline issues. It will take 138 HM III and 138 HM II Subjects (276 total Subjects) to achieve 80% power to prove the HM III is non-inferior to HM II when the margin of non-inferiority is -10% ($=\Delta$ in the above null and alternative hypotheses) using the Farrington-Manning risk difference approach to non-inferiority at a one-sided alpha = 0.025.

INTERMACS HM II data from 26 sites likely to participate in the HM III IDE study was reviewed. Eight hundred and twenty (820) patients were implanted with the HM II in 2012 at these sites and 52 (6%) received a transplant or explant due to myocardial recovery prior to 6 months. In order to have sufficient data to evaluate the 6 month success rate, an additional 9 Subjects will be randomized per arm (6% of 138) to account for these early outcomes. This results in a total of 147 Subjects randomized in each arm (294 total Subjects).

